### Project Summary:

Methamphetamine (MA) has re-emerged as the next substance use crisis in the United States. Unlike the opioid crisis, treatment of MA use disorder is significantly more challenging without an FDA-approved medication. Most of the candidate drugs tested to date focus on modulating monoaminergic pathways, yielding limited evidence of benefit. New interventions aimed at novel biological mechanisms are needed.

Converging evidence highlights the orexin system as a promising target for addressing key mechanisms in the recovery from substance use disorders, including regulating sleep architecture, buffering hyper-arousal and stress responses, and modulating reward processing and drug-motivated behaviors. Activation of orexin (OX) receptors by psychostimulant drugs mediates arousal (OX2R) and reward (OX1R) functions and, by contrast, blockade of both receptors produces attenuation of these physiological and behavioral functions. In preclinical animal models, selective OX1R / OX2R receptor antagonism has been shown to reduce MA self-administration and MA-induced reinstatement responding. In humans with cocaine use disorder, we demonstrated that treatment with the FDA-approved dual orexin receptor antagonist suvorexant (SUVO) improved outcomes in relapse-related domains of sleep, stress, and cue reactivity. Here, we propose to expand these promising findings by examining the effects of SUVO in humans with MA use disorder, an understudied clinical population for whom there is no currently approved treatment indication.

The primary goal of the study is to assess the effects of SUVO on physiological sleep (actigraphy, EEG) and self-reported sleep quality. We will also assess two other domains linked to the orexin system and commonly related to MA relapse including stress and cue reactivity/craving. Our overarching hypothesis is that treatment with SUVO will attenuate disruptions in sleep, stress, and cue reactivity/craving. By engaging these relapse-related target mechanisms, this work will provide critical proof-of-concept evidence for a subsequent R01. To that end, we will employ a within-subjects, two group cross-over design (N=12) and take a multimodal approach to assessing sleep, stress, and cue reactivity/craving. Participants will complete stress reactivity and electroencephalogram (EEG) laboratory tasks, self-report, and drug use measures after one week of SUVO, washout, and placebo (PL), order counterbalanced between groups. Participants will also wear an activity watch at night in order to have their sleep monitored via actigraphy.

### Primary Hypotheses and Specific Aims:

Primary Aim 1: Determine the effects of SUVO on sleep, stress, and cue reactivity/craving

Hypothesis 1a: SUVO compared to placebo will improve sleep outcomes assessed by actigraphy (total sleep time, wake after sleep onset), self-report (Pittsburg Sleep Quality Index), and EEG (resting state alpha power);

Hypothesis 1b: SUVO compared to placebo will improve acute stress reactivity as measured by physiological responses (cold-pressor task induced cortisol and HR/BP) and subjective ratings (Visual Analog Scale; Depression Anxiety Stress Scale).

Hypothesis 1c: SUVO compared to placebo will reduce cue reactivity/craving as measured by LPP to methamphetamine images and self-report (Brief Substance Craving Scale).

Exploratory Aim 2: Evaluate the preliminary safety and side effects profile of SUVO.

**Primary outcome measures:** self-reported sleep, resting state alpha power, LPP, self-reported stress, and cortisol measured at each study visit after 1-week of SUVO, washout, and PL; total sleep time and wake after sleep onset measured nightly via actigraphy watch

**Secondary outcome measures:** methamphetamine use (TLFB and UDS) measured at each study visit after 1-week of SUVO, washout, and PL; side effects questionnaire, BDI, and CSSRS measured at each study visit after 1-week of SUVO, washout, and PL

## Background and Rationale:

Public health significance of MA use disorder. MA use disorder 1) is surging in recent years, contributing to a massive (~180%) increase in overdose related MA deaths from 2015-2019, 2) presents a tremendous economic burden to society (likely >\$48 billion/year), and 3) leads to severe impacts on physical/mental health and social functioning.

The role of sleep, stress, and cue reactivity in addiction. MA use has marked effects on several interconnecting neurobiological processes such as sleep, stress, and cue reactivity. Chronic MA use and MA withdrawal is associated with poorer sleep quality. Severe sleep disturbances can aggravate MA use disorder symptoms, such as drug craving and stress, and are commonly a large barrier to treatment success. Similarly, stress is a critical part of the initiation and maintenance of addiction, e.g., use of substances to alleviate negative mood states. Stress and anxiety are known to trigger cravings and use of drugs of abuse in turn activates stress pathways, which together can increase vulnerability to cue-induced relapse. Cue reactivity is a hallmark feature of addiction, where previously innocuous stimuli become associated with drug reward and acquire incentive properties. Cue-induced craving is central to addiction and can continue to occur during abstinence, triggering relapse. Taken together, a medication targeting sleep, stress, and/or cue reactivity would be of interest in treating MA and other substance use disorders.

Objective measurement of critical processes. Research suggests that subjective measures may not capture the substantial heterogeneity in risk for relapse, especially in persons with substance use disorders, who may lack insight. Further, despite longstanding debate in the literature, there is no accepted self-report measure of craving. Recognizing these limitations, the current study will take a multi-modal approach to measuring relevant constructs related to use and relapse. First, sleep measurement will be enhanced by leveraging actigraphy methods in addition to self-reported sleep. While including a neuroimaging measure during sleep is out of the scope of the current study, waking effects on sleep disruptions will also be assessed with resting state electroencephalogram (EEG). For stress, salivary cortisol and heart rate/blood pressure assessments will be taken before and after induction of stress with the cold pressor task. Finally, cue reactivity and craving will be assessed both with self-report and the late positive potential (LPP), an EEG component that reflects the motivational relevance of a stimulus.

Orexin system as a novel target for MA treatment. One system that has been neurobiologically linked to regulating these processes is the orexin system. Orexins are a class of amino acid peptides that are sourced in the hypothalamus for which two receptors have been discovered (OX1R, OX2R). Orexins are neuromodulators: they exert their effects through regulation of GABA and glutamate. While the orexin system is widely known for regulating appetite and arousal/sleep, it has widespread connections throughout the brain and is now known to modulate a wide variety of other behaviors including stress, reward-seeking behaviors, and reactivity to reward cues. Critically, recent evidence indicates that selective OX1R/OX2R receptor antagonism reduced MA self-administration/MA-induced reinstatement responding as well as blocked MA-induced hyperarousal and sleep impairment in preclinical studies. While pharmacological interventions in animal models studies show promise, medication development for MA use disorder has largely failed. However, there is one FDA-approved orexin compound indicated for the treatment of insomnia: Suvorexant (SUVO), a dual orexin receptor antagonist. FDA-approval of suvorexant for the treatment of insomnia helps pave the way for rapidly advancing the development of orexin-based therapies for the treatment of MA use disorder and other addictions. In the current study participants will receive SUVO and placebo in a cross-over design, have their sleep measured via actigraphy, undergo an EEG assessment, and complete laboratory tasks to assess stress and MA cue reactivity.

## Methods:

**Overall study design.** We will use a two-group cross-over design. Each group will complete three conditions, each lasting one week. 12 participants will be randomized to one of the two groups. Group one (n=6) will receive one-week placebo, one-week washout, and one-week SUVO. Group two (n=6) will receive one-week SUVO, one-week washout, and one-week placebo. During the washout period, the participants will not receive any pills. Eligibility criteria and baseline measures will be collected on Day 0 before the start of week one. Participants will come to the clinic once a week on Monday for 4 weeks. On Day 1 (Monday) of the first week, the participants will receive their medication and actigraphy watches. Each following Monday, they will complete self-report and drug use measures, as well as the laboratory tasks (cold pressor and EEG). Table 1 outlines the schedule of assessments. We will aim to enroll a total of 16 participants to complete 12, with dropouts being replaced, if possible.

**Participants, Recruitment, and Setting.** The participants will consist of non-treatment-seeking individuals meeting DSM-5 criteria for MA use disorder. All participants will be between the ages of 18-45 and fluent in English. IRB NUMBER: HSC-MS-22-0796 IRB APPROVAL DATE: 10/09/2023

Individuals will be excluded if they meet the following criteria: presence of an alcohol use disorder (AUD), reporting binge drinking (>7 drinks for women and >14 drinks for men), greater than mild substance use disorder on any other illicit drug; any medical conditions contraindicating SUVO (e.g., severe pulmonary disease, severe cardiovascular disease or clinically abnormal ECG, severe liver or kidney disease, seizure disorder, or sleep disorder – particularly narcolepsy); currently taking medications with known drug interactions with SUVO (e.g., MAO inhibitors, anticonvulsants, haloperidol, phenothiazines, anesthetics, and any sedative); pregnant or breast feeding; current DSM-5 psychiatric disorder or neurological disease requiring on-going treatment that would make participation unsafe; history of seizure disorder; head injury with loss of consciousness in the last 5 years. Eligibility criteria will be assessed at baseline and will be conducted by licensed counselors and the medical director ([name]). The study will be conducted at the Center for Neurobehavioral Research on Addiction (CNRA), where the PI ([name]) and Co-Is (Drs. [name], [name], [name]) have experience conducting treatment and laboratory-based studies in substance use populations. Recruitment will follow typical CNRA protocols, including local advertising in print/radio, recruitment companies (Build Clinical/TrialFacts) and referrals from prior CNRA studies and the Houston area. Data analyses will be performed by [name], a biostatistician also affiliated with the CNRA, with expertise in the application of quantitative methods to investigate experimental and clinical outcomes related to EEG, sleep, and psychostimulant use.

	0 (Intake)	1 (PL or SUVO)						2 (washout)						3 (PL or SUVO)						4 (Final)			
		M	T	W	R	F	S	S	M	T	W	R	F	S	S	M	T	W	R	F	S	S	
Study Day	M-F																						M
Consent and Baseline Screening (UDS, SCID, ASI, KMSK, TLFB, physical/ psychiatric eval)	x																						
Receive Study Medication (SUVO or PL)		x	x	x	x	x	x	x								x	x	x	x	x	x	x	x
Medication Compliance		x	x	x	x	x	x	x								x	x	x	x	x	x	x	x
Actigraphy		x	x	x	x	x	x	x	x	x	x	x	x	x	x	x	x	x	x	x	x	x	x
Self-report Sleep, Stress, Craving, MA use (PSQI, ISS, PROMIS-SF, DASS, VAS, BSCS, BDI, TLFB), and UDS									x							x							x
Laboratory Tasks (Cold Pressor, EEG)									x							x							x

**SCID** - Structured Clinical Interview for DSM-5, **ASI** - Addiction Severity Index; **KMSK** - Kreek-McHugh-Schluger-Kellogg scale; **TLFB** - Timeline Followback; **PSQI** – Pittsburg Sleep Quality Index; **ISS** – Insomnia Severity Index; **PROMIS-SF** – Patient Reported Outcomes Measurement Information System Short Form Sleep Disturbance; **BDI** – Beck’s Depression Inventory; **DASS** – Depression Anxiety Stress Scale; **VAS** – Visual Analogue Scale of Stress; **BSCS** – Brief Substance Craving Scale.

**Payment and Compensation.** Participants will receive \$40 for the baseline evaluation. As methamphetamine users tend to live further outside the city, we are budgeting extra for bus/parking validation/rideshare options, up to \$30 per visit. Participants will receive \$50 for each laboratory visit (3 visits total) and a completion bonus on their final visit for \$50. If medication compliance is reached, participants will receive an extra \$10 at each clinic visit (for more information see Medication Compliance).

**Baseline Screening.** As a part of the CNRA general evaluation protocol (HSC-MS-0322), participants will receive a full physical and psychiatric evaluation on the first day including: a medical-history questionnaire, physical examination, urine drug screen (UDS), pregnancy test, blood draw, and ECG. Clinicians will administer the SCID, the ASI, the KMSK, and TLFB to assess current diagnoses, severity, chronicity, and daily use of MA (Table 1). UDS will be used to assess eligibility and substance use at baseline as well as on EEG testing days. It will also be used to assess medication compliance.

**Medication.** Suvorexant (Belsomra®) is a dual orexin receptor antagonist and an FDA-approved medication for the treatment of insomnia. Prior research in humans indicates it is safe in human populations. While this would be the first study assessing SUVO in MA users, a prior study from our group indicated that SUVO was safely administered to individuals with cocaine use disorder. Our prior study used a conservative 2-week dose titration schedule (Week 1: 10mg; Week 2: 20mg), with no serious adverse effects reported or observed. In the current study, participants will receive 20mg of SUVO for 7 days, the highest allowed FDA dose. Study medication will be compounded by CNRA pharmacists using size 00 capsules. Each dose will contain 20mg (active medication) or 0mg (placebo) of suvorexant, 25mg of riboflavin, and cornstarch filler. The half-life is about 12 hours on average and steady-state plasma concentrations occur in 3 days with daily administration. Due to the hypnotic **IRB NUMBER: HSC-MS-22-0796** **UTHealth Houston** **THE DRUG PROVIDED TO THE SUBJECT WILL BE** **09/2023**

directed to take the medication at 10:00PM.

**Medication Compliance.** Because SUVO will be administered in the evening at 10:00 PM, compliance is a high priority. Compliance will be assessed with CAROMA (cell-phone assisted remote observation of medication adherence). Participants record short videos of themselves taking the medication and send it to the CNRA study cell phone or save the videos to show study staff in person. Riboflavin will be added to medication capsules and urine ultraviolet fluorescent tests will be conducted at the weekly clinic visit to assess compliance. Text-based medication reminders with required text replies (Y/N) will also be used. If CAROMA, pills count, riboflavin readings, and text replies agree, then participants will be paid \$10 per visit for compliance. Payments are adjusted downward if the measures do not agree. Specifically, if compliance is reached for 7 days, then the participant will receive the full \$10, up to 6 days: \$7, up to 4 days: \$5, up to 2 days: \$3, less than 2 days: \$0.

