**Cue Reactivity/Craving (LPP).** The late positive potential (LPP) is an event-related potential component thought to reflect the motivational relevance of visual stimuli. The LPP to drug images is enhanced in drug users compared to controls, is correlated with craving, and tracks with abstinence, thus serving as an objective measure of cue reactivity/cue-induced craving. EEG will be collected on test days prior to the cold pressor task. The Picture Viewing Task will be used to elicit the LPP. Suvorexant might lead to decrease drug use through reducing reactivity toward drug cues. Therefore, the picture viewing task will provide this neural assessment of cue reactivity. In the task, the participants view images in four categories, pleasant, unpleasant, methamphetamine, and neutral. The other image categories are necessary, so that we can ensure the brain reactivity is specifically in response to drug images and not just salient images. This is a standard task used in the EEG literature and a meta-analysis shows drug users have an increased

response to drug images with a large effect size.

**Cue Reactivity/Craving (Self-Report).** The Brief Substance Craving Scale (BSCS) will be used to assess current MA craving. The BSCS will be assessed on each test day prior to laboratory tasks.

**Safety/Side Effects.** A 31-item questionnaire will be administered on each test day to assess side effects and adverse events. The Colombia Suicide Severity Rating Scale (CSSRS) and Beck's Depression Inventory (BDI) will be administered at each visit per NIH guidelines. Breath alcohol concentration will also be assessed at each visit to assess for current intoxication.

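### No safety contact is scheduled after the final Monday visit, so the placebo-first group is assessed only once after starting suvorexant, about half a day after its last dose

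*Combined protocol and SAP*

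**What the plan says.** **Sequences.** Under Methods, Overall study design: "Group one (n=6) will receive one-week placebo, one-week washout, and one-week SUVO". For the other sequence: "Group two (n=6) will receive one-week SUVO, one-week washout, and one-week placebo".

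**Visits.** "Participants will come to the clinic once a week on Monday for 4 weeks". Table 1 labels the last of these as final; it is the Monday that closes the second treatment week.

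**Dosing.** The Medication paragraph says "participants will receive 20mg of SUVO for 7 days" and "The half-life is about 12 hours on average and steady-state plasma concentrations occur in 3 days with daily administration". Medication Compliance adds the clock time: "Because SUVO will be administered in the evening at 10:00 PM".

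**Safety data.** Measures, Safety/Side Effects: "A 31-item questionnaire will be administered on each test day to assess side effects and adverse events". The secondary outcome list places the questionnaire, BDI and CSSRS at the visits after the SUVO, washout and placebo weeks. Adequacy of Protection Against Risks provides for weekly adverse event (AE) review. No later visit, call or AE window is given.

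**Analysis.** Specific Hypothesis Testing, Aim 2, describes AE frequency between and within conditions and models specific AEs by condition.

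**Table 1.** The row that begins "Receive Study Medication (SUVO or PL" and the compliance row each carry 7 marks in week 1, none in washout and 8 in the second period. The eighth is in the final-Monday column.

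**The concern.** Aim 2, which is exploratory, is a preliminary safety and side-effect profile of SUVO, and the protocol says this is the first study of the drug in methamphetamine users. The section on potential risks includes worsening depression and suicidal thinking, and a rise in suicidality on the CSSRS leads to removal and referral. In the placebo-first group that scale is applied once after SUVO begins and not again on any schedule. An effect that appears or persists after stopping can be actively picked up in one sequence only.

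The same asymmetry reaches the analysis. The washout week follows SUVO in one sequence and placebo in the other. An AE comparison that treats washout as a single condition pools post-SUVO with post-placebo observation, and the post-SUVO week has no counterpart in the placebo-first group.

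**Working it through.** The plan gives no figure of its own on this point, so there is none to reproduce.

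**Step 1. Time from last dose to last assessment, placebo-first group.** Inputs: 7 doses from Monday to Sunday and the 10 PM dose time (Medication, Medication Compliance); final visit on the next Monday (Overall study design, Table 1). Clinic hours are not stated; I assume 08:00 to 17:00. From Sunday 22:00 the interval is 2 + 8 = 10 h to 2 + 17 = 19 h.

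**Step 2. Fraction of that last dose remaining.** With the stated half-life of about 12 h, fraction = 0.5^(t/12).
- t = 10 h: 0.5^(10/12) = 0.56
- t = 19 h: 0.5^(19/12) = 0.33
- 5% is reached at 12 × log2(20) = 51.9 h, about 02:00 on Wednesday, which is 33 to 42 h after the visit (52 − 19 and 52 − 10).

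**Step 3. The SUVO-first group.** Its post-SUVO visit has the same timing. Its washout visit is a week later: at 09:00, 7 × 24 + 11 = 179 h after the last dose, or 179/12 = 14.9 half-lives. A further visit follows after the placebo week. Scheduled observation after stopping SUVO thus covers 6 of 12 planned completers.

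**Step 4. What 6 rather than 12 observed means.** Chance of at least one event = 1 − (1 − p)^n. The rates p are assumptions; the documents give none.

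| Assumed rate p | n = 6 | n = 12 |
|---|---|---|
| 5% | 1 − 0.95^6 = 26.5% | 1 − 0.95^12 = 46.0% |
| 10% | 1 − 0.90^6 = 46.9% | 1 − 0.90^12 = 71.8% |
| 20% | 1 − 0.80^6 = 73.8% | 1 − 0.80^12 = 93.1% |

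If no event is seen, the one-sided 95% upper bound, 1 − 0.05^(1/n), is 39.3% with 6 and 22.1% with 12.

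**Step 5. Table 1 against the text.** The marks total 7 + 8 = 15; two 7-day periods give 14. The eighth mark lines up with the final-Monday mark in the laboratory row. If it denotes a dose at the stated hour, that dose would come after the last scheduled assessment.

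**The case against.** **A reader might infer that safety collection stops at the final visit.** The documents do not say so. The Data Safety and Monitoring Plan describes an ongoing AE log with no closing date, and participants are told to inform clinic staff of side effects that continue or get worse. What is missing is scheduled, active contact. Passive reporting is not equivalent to the questionnaire and CSSRS that the SUVO-first group receives.

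**A reader might infer that next-day impairment goes unchecked.** It does not. Adequacy of Protection Against Risks requires an impairment battery at the end of each experimental day, before release. Both sequences also have the SUVO week itself covered by the Monday assessment that follows it, so on-drug ascertainment is balanced.

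**A reader might infer that a 15th dose is planned.** Table 1 alone cannot carry that. The text says one week and 7 days, the compliance payment scale tops out at 7 days, and the actigraphy row is marked on the final Monday too, so the mark may be a table slip or a visit-day activity. Against the visit-day reading, the Monday after week 1 has no such medication or compliance mark. The conflict stands; its meaning is open.

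**The gap can be called small.** By the stated half-life, the unobserved elimination phase is about a day and a half. This is a 12-completer pilot of an approved drug given for 7 days, the documents name no withdrawal or rebound risk, and the AE log rates each event's relationship to drug, so a washout-week event need not be lost to SUVO. All of this limits severity. It does not supply a scheduled assessment for the placebo-first group, and relatedness ratings do not separate the two kinds of washout week in a by-condition table.

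**Conclusion.** The concern holds for scheduled, active follow-up. Six of 12 planned completers have a single scheduled safety assessment after starting SUVO, at about half a day and with roughly 56% to 33% of the last dose remaining; the other six have two further weekly assessments. The affected events are delayed, persisting or post-stopping ones, including mood and suicidality. The chance of seeing at least one such event is lower by about 19 to 25 percentage points across assumed rates of 5% to 20% (46.0 − 26.5 = 19.5; 71.8 − 46.9 = 24.9; 93.1 − 73.8 = 19.3). The by-condition AE comparison also mixes post-SUVO and post-placebo washout weeks.

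This rests on seven doses ending on Sunday, visits between 08:00 and 17:00, simple exponential decline at the stated half-life, and full completion with 6 per sequence (up to 16 may be enrolled). It is worth correcting because the remedy is cheap. It does not threaten the efficacy analyses. The Table 1 mismatch is a separate item for reconciliation.

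**What to change.** 1. Add one telephone safety contact after the final visit for every participant in both sequences, using the existing side-effect questionnaire and CSSRS screen. The sponsor should set the timing so that it falls after drug elimination.
2. State when AE collection closes.
3. In the Aim 2 tables, split washout-week events by preceding treatment: post-SUVO and post-placebo. Show the post-SUVO contact from the placebo-first group alongside the former.
4. Reconcile the final-Monday medication and compliance marks in Table 1 with the 7 days in the Medication paragraph.

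Cost: at most 16 calls by existing staff, a small amendment, one further table split and a checked schedule. Some calls will go unanswered, so the number reached should be reported as the denominator. Treatment, randomisation and the efficacy analyses are unchanged.
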